3.3 Definition of Baseline values

Baseline for all study outcomes will be determined using different methods depending on whether the subject is LTFU or DE.

Unless otherwise specified, Baseline values will be determined as follows:

- DE subjects: the last (most recent) available pre-dose measurement of the corresponding outcome will be used as Baseline
- LTFU subjects:
 - if available, Baseline values from the previous BRV core studies will be used as Baseline
 - otherwise the last (most recent) available measurement assessed between day of final on-treatment measurement in core study and the day before first BRV administration in N01266 will be used as Baseline

For laboratory parameters, vital signs (systolic blood pressure [SBP], diastolic blood pressure [DBP], and pulse rate), body weight, and ECGs, Baseline values will be determined as follows:

- DE subjects: the last (most recent) available pre-dose measurement of the corresponding outcome will be used as Baseline
- LTFU subjects: the last (most recent) available scheduled or UV assessment up to the day of subjects first BRV administration in core study will be used as Baseline (most recent measurement up to first BRV administration in core study, not in N01266 as in the general definition of Baseline values)

Baseline will be determined separately for each individual clinical laboratory parameter for hematology, biochemistry, endocrinology and urinalysis assessments.

3.4 Protocol deviations

Important protocol deviations are deviations from the protocol which could potentially have a meaningful impact on either the primary outcome of safety and tolerability of BRV, or the secondary outcome of efficacy of BRV for an individual subject. The criteria for identifying important protocol deviations and the classification of important protocol deviations will be defined separately in project Data Cleaning Plan. To the extent feasible, rules for identifying protocol deviations will be defined without review of the data and without consideration of the frequency of occurrence of such deviations. Whenever possible, criteria for identifying important

protocol deviations will be implemented algorithmically to ensure consistency in the classification of important protocol deviations across all subjects.

Important protocol deviations will be reviewed as part of the ongoing data cleaning meetings prior to DBL to confirm exclusion from analysis sets.

3.5 Analysis sets

Disposition will be summarized for Enrolled Subjects. Safety variables will be summarized using the Safety Set (SS) and efficacy variables will be summarized using the Full Analysis Set (FAS).

3.5.1 Enrolled Subjects

Enrolled subjects will consist of all subjects with epilepsy who gave informed consent, or for whom informed consent was given by parent(s)/legal representative(s).

3.5.2 Safety Set

The SS will consist of all enrolled subjects who took at least 1 dose of study medication in this long-term study.

3.5.3 Full Analysis Set

The FAS will be used for the analysis of seizure data and will consist of all subjects in the SS, who have at least 1 completed post-Baseline DRC or EEG.

3.6 Treatment assignment and treatment groups

The following table displays the planned titration schedule of BRV for DE subjects during the study:

Table 3-5: Recommended BRV dosing schedule for DE subjects in the Up-Titration Period

Week	Dose per dosing occasion (mg/kg)	BRV dose per day (mg/kg/day)
TV1 (1)	~0.5	~1.0
TV2 (2)	~1.0	~2.0
TV3 (3)	~2.0	~4.0

BRV=brivaracetam; TV=Titration Visit; "≈"=approximately

Daily doses will not exceed the maximums of 50mg/day, 100mg/day, and 200mg/day for Weeks 1, 2, and 3 of up-titration, respectively.

3.7 Site pooling strategy

The number of enrolled subjects for most sites is expected to be low. In general, it will not be feasible to adjust statistical analyses for site effect and there are no plans to present any study outcomes by site. No site pooling strategy is defined for this study.

3.8 Coding dictionaries

Medical history and AEs will be coded using the Medical Dictionary for Regulatory Activities (MedDRA®). Medications will be coded using the World Health Organization Drug Reference List (WHO-DRL). Prior and concomitant medical procedures will not be coded; the reported procedures will be retained in the study database.

3.9 Possible clinically significant treatment-emergent (PCST) values

Possible clinically significant treatment-emergent values are any laboratory values, vital signs, or ECG parameters meeting the criteria defined in Appendix Section 12.1 which occur any time after screening and after the first dose of BRV has been taken. The PCST criteria will only be applied to analytes that were routinely collected as designated in the protocol. A list of analytes that were to be routinely collected is provided Section 9.2.1 of the protocol.

PCST criteria are based on the FDA Division of Neuropharmacological Drug Products guidelines with some UCB-defined additions.

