3.2 General study level definitions

3.2.1 Analysis time points

3.2.1.1 First and final dose of study drug

Unless otherwise noted, all references to the first dose of study drug in this SAP refer to the first dose of study drug during N01266 (i.e., not the first dose of study drug from the core study in which subjects participated prior to N01266 for LTFU subjects). Unless otherwise noted, all references to the final dose of study drug in this SAP refer to the final dose of study drug taken across all study periods (ie, the final dose of study drug across the Up-Titration, Evaluation, and Down-Titration Periods).

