The number and percentage of subjects with any post-Baseline PCST value, any PCST low value, and any PCST high value for hematology, biochemistry and urinalysis will be summarized for the Evaluation and Safety Periods separately and for the Evaluation and Safety Period combined by laboratory parameter overall and by age group. PCST criteria for hematology and biochemistry are presented in Appendix Section 12.1 A urinalysis value is considered PCST abnormal if an upward shift of at least 2 degrees from the Baseline occurs under investigational treatment. Percentages will be relative to the number of subjects with an on-treatment assessment.

Observed values and change from Baseline value tables will only present scheduled visits, whereas for PCST tables, values reported at an UV will be summarized under the preceding scheduled visit if the abnormality was not already reported at the preceding scheduled visit. Treatment emergent for this analysis includes any PCST laboratory abnormalities observed during the Evaluation Period.

A subject number table will be provided that identifies subjects with a PCST finding after the first dose of BRV for each type of laboratory abnormality.

All laboratory parameters (planned and unplanned parameters and assessed on scheduled and unscheduled visits) will be provided in subject data listings.

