12.3 PCST Criteria for Vital Signs

Parameter (Unit)	Age Range	Abnormality criteria
Pulse Rate (beats/minute)	<6m	<100 >180
	$\geq 6m - < 3y$	<90 >150
	$\geq 3y - < 12y$	<60 >130

Parameter (Unit)	Age Range	Abnormality criteria
	$\geq 12y - < 17y$	<50 >120
Systolic Blood Pressure (mmHg)	<6m	<60 >100
	$\geq 6m - < 3y$	<70 >120
	$\geq 3y - < 12y$	<80 >140
	$\geq 12y - < 17y$	<90 >160
Diastolic Blood Pressure (mmHg)	<6m	<40 >65
	$\geq 6m - < 3y$	<45 >75
	$\geq 3y - < 12y$	<50 >80
	$\geq 12y - < 17y$	<50 >105
Body Weight	1m - <17y	<3% or >97% of the normal body weight growth curve ranges based on gender and the age of subject on date of weight assessment
	$\geq 17y$	A decrease/increase from Baseline of $\geq 10\%$

m=month, y=year.

Note: A month is defined as 30 days; a year is defined as 365.25 days.

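### Most PCST criteria have no Baseline condition, so abnormalities that pre-date BRV count as treatment-emergent, and the laboratory PCST percentages leave out Up-Titration

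*SAP*

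**What the plan says.** Section 3.9 calls a laboratory value, vital sign or ECG parameter PCST if it meets the appendix criteria at a time "which occur any time after screening and after the first dose of BRV has been taken". Under section 3.2.1.1, references to the first dose, unless otherwise noted, "refer to the first dose of study drug during N01266". For long-term follow-up (LTFU) subjects the clock therefore starts after BRV has already been taken in the core study.

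The limits in section 12.1 (hematology, biochemistry) and most of those in section 12.3 (pulse, SBP, DBP, body weight under 17 years) are absolute. For weight under 17 years the criterion is below 3% or above 97% "of the normal body weight growth curve ranges based on gender and the age of subject on date of weight assessment". Two criteria are relative to Baseline. In section 8.3, "A urinalysis value is considered PCST abnormal if an upward shift of at least 2 degrees from the Baseline occurs under investigational treatment", and in section 12.3 weight at 17 years or older needs a change from Baseline of at least 10%.

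Section 3.3 derives a pre-BRV Baseline for laboratory parameters, SBP, DBP, pulse and weight. For LTFU subjects it is "the last (most recent) available scheduled or UV assessment up to the day of subjects first BRV administration in core study".

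On periods, section 8.3 says laboratory PCST values "will be summarized for the Evaluation and Safety Periods separately and for the Evaluation and Safety Period combined by laboratory parameter", over a denominator of subjects with an on-treatment assessment. It then adds: "Treatment emergent for this analysis includes any PCST laboratory abnormalities observed during the Evaluation Period".

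**The concern.** The tables are labelled treatment-emergent, but for most parameters nothing in the definition separates an abnormality that arose on BRV from one that was there before it. In a single-arm study whose primary objective is long-term safety and tolerability, the subject's own Baseline is the only internal reference. If it is not used, the percentage mixes new abnormality with pre-existing disease and with long-standing effects of other treatment.

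The window raises a second problem. Section 3.9 counts from the first dose onward, whereas section 8.3 names two periods, and Up-Titration, when directly enrolled (DE) subjects first meet the drug, is not one of them. A reader of the laboratory PCST percentages would not see abnormalities that arose and resolved during those first weeks.

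**Working it through.** The SAP states no PCST rate and no sample-size basis, so there is no figure to reproduce. The check is a comparison of definitions, followed by an illustration.

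**1. Is there a Baseline condition?**

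| Criterion | Limit | Uses Baseline value? |
|---|---|---|
| Hematology, biochemistry (12.1) | absolute, by age band | no |
| Pulse, SBP, DBP (12.3) | absolute, by age band | no |
| Body weight, under 17 y (12.3) | growth-curve limits | no |
| Body weight, 17 y or older (12.3) | change of 10% or more | yes |
| Urinalysis (8.3, 12.2) | upward shift of 2 degrees or more | yes |

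In 8.3 and 8.4.1, post-Baseline describes when a value was taken. It does not require a normal Baseline. Neither section plans a categorical shift table for hematology, biochemistry or vital signs.

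**2. Body weight under 17 y.** Reading the limits as the 3rd and 97th centiles, a reference population has 3% + 3% = 6% outside them at any single assessment. If all of about 600 subjects were under 17 and followed the reference curve (an assumption), that is 0.06 × 600 = 36 subjects with no drug effect. Section 8.4.1 also stratifies the table by Evaluation Period visit, so a child with a stable centile outside the limits is flagged at each one.

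**3. General size.** Let b be the share meeting a limit at Baseline, s the share of those still meeting it on treatment, and i the new on-treatment incidence among the rest.

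- Rate as written: b·s + (1 − b)·i
- Rate among subjects not abnormal at Baseline: i
- Excess: b·(s − i), close to b·s when i is small
- Share of flagged subjects who were already abnormal: b·s / [b·s + (1 − b)·i]

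All inputs below are assumptions.

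| b | s | i | Rate as written | Already abnormal |
|---|---|---|---|---|
| 2% | 50% | 2% | 3.0% | 34% |
| 2% | 50% | 5% | 5.9% | 17% |
| 5% | 90% | 2% | 6.4% | 70% |
| 10% | 90% | 2% | 10.8% | 83% |
| 10% | 90% | 5% | 13.5% | 67% |

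Over b = 2–10%, s = 50–90% and i = 2–5%, the excess runs from 0.02 × (0.50 − 0.05) = 0.9 to 0.10 × (0.90 − 0.02) = 8.8 percentage points.

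**4. Windows.** By section 3.2.3, Up-Titration (DE subjects only) starts at the first BRV dose, and the Safety Period starts the day after the last.

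| Output | Up-Titration | Evaluation | Safety (off drug) |
|---|---|---|---|
| 3.9 definition | in | in | in |
| 8.3 laboratory PCST percentages | out | in | in, over an on-treatment denominator |
| 8.3 treatment-emergent statement | out | in | out |
| 8.3 laboratory subject number table | in | in | in |
| 8.4.1 vital-sign PCST percentages | separate summary | in | out (stops at final dose) |

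Laboratory data from Up-Titration do exist, because 8.3 repeats the observed-value and change summaries for those visits.

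**The case against.** The best defence is that these outputs are descriptive and secondary. The primary variables are TEAEs and serious TEAEs, while laboratory tests, vital signs and weight are other variables. Baseline is not ignored either, since changes from Baseline are summarized for laboratory parameters, SBP, DBP and pulse. All of that is correct and limits the consequence. It does not rescue the PCST percentage, because a mean change cannot show how many subjects crossed a limit on treatment.

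Several stronger readings are tempting, but the document does not support them.

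- **Up-Titration laboratory abnormalities go unreported.** They do not. The subject number table covers PCST findings after the first dose and all laboratory values are listed. Only the incidence percentage is missing, and only for DE subjects (at least 100 of about 600).
- **Down-Titration laboratory findings are lost.** The period is not named in the laboratory PCST summary, but the SAP does not show that laboratory samples are scheduled then. An unscheduled value may also be carried to the preceding scheduled visit.
- **The ECG section shows how PCST should be handled in Up-Titration.** Section 8.4.2 summarizes the investigator's judgement of abnormality rather than PCST. Vital signs are the valid comparison.
- **A specific number of points in the weight table is spurious.** That needs this population's Baseline prevalence and persistence, and neither is given.
- **A Baseline condition would remove concomitant-AED effects.** It would not remove effects of AEDs added or changed later, which the plan allows at any time.

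A bare exclusion rule would also have a fault of its own, because a subject slightly beyond a limit at Baseline who then worsens markedly would drop out of the emergent count. The remedy has to keep such subjects visible.

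**Conclusion.** The point holds in two parts. First, for hematology, biochemistry, pulse, SBP, DBP and body weight under 17 years, an abnormality that pre-dates BRV is counted as treatment-emergent. This follows from the text and needs no assumption. Its size in this trial is unknown. The 6% for weight is a reference-population figure at one assessment and rests on reading the limits as centiles; the range of 0.9 to 8.8 points is illustrative only.

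Second, 3.9 and 8.3 disagree on the treatment-emergent window. As a result, DE subjects' Up-Titration laboratory abnormalities enter no incidence percentage, while the off-drug Safety Period is reported over subjects with on-treatment samples.

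The change should be made before the tables are produced. The percentages would be mislabelled and incomplete, but no primary variable is affected, and the underlying data can be recovered from the subject number table and listings.

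**What to change.** 1. In 3.9, 8.3 and 8.4.1, for criteria with no Baseline term, count a subject as emergent only if the section 3.3 Baseline did not meet the same-direction limit. Apply the age band at the Baseline assessment, treat a missing Baseline as not meeting the limit, and state the denominator. Leave urinalysis and weight at 17 years or older as they are.
2. Show subjects abnormal both at Baseline and on treatment in a separate row, or provide a Baseline-by-worst-on-treatment shift table. Either keeps worsening from an abnormal Baseline in view.
3. Give 3.9 and 8.3 one treatment-emergent window. Repeat the laboratory PCST summary for Up-Titration in DE subjects, as 8.4.1 does for vital signs, and include on-drug Down-Titration values if any are collected.
4. Report the Safety Period over subjects with a Safety Period assessment.

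The cost is SAP wording, one extra merge and a few more table rows. Baseline values are already derived and no new data are needed.

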3.10 Definitions of study-specific derived variables

3.10.1 Definition of treatment-emergent AE

AEs will be classified as either pre-treatment or treatment emergent. In the following definitions, first dose of BRV refers to the first dose in N01266 (i.e., not the first dose of BRV from the core study in which subjects participated prior to N01266 for LTFU subjects). Pre-treatment AEs are defined as AEs which had an onset date at least one day prior to the first dose of BRV.

Treatment-emergent adverse events (TEAEs) are defined as AEs that had onset on or after the day of first BRV dose. AEs with an incomplete onset date will be classified as TEAEs if the month and year of onset (when only the month and year are specified) is the same or after the month and year of the first BRV dose or the year of onset (when only the year is specified) is the same or after the year of first BRV dose. AEs with a missing onset date will also be classified as TEAEs provided the subject received at least one dose of BRV.

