8.2.2 Incidences of TEAEs

Incidence summaries will be presented by SOC and PT. These tables will include the number and percentage of subjects and number of events by SOC and PT. For the number of subjects by PT, if a subject experiences multiple AE within the same PT, then that PT will only be counted once. As with the PT, for the number of subjects by SOC, if a subject experiences multiple AEs within the same SOC, then that SOC will be counted only once. Percentages will be calculated out of the number of subjects at risk in the SS unless otherwise stated.

Incidence tables are sorted alphabetically by SOC and decreasing by frequency in PT in the overall column. In case of ties, PTs are sorted alphabetically.

The following TEAE summaries will be presented:

- Incidence of TEAEs

- Incidence of TEAEs by 3-month time interval (one table presenting TEAEs starting within time intervals and one presenting those ongoing in the time interval)
- Incidence of drug-related TEAEs by 3-month time interval
- Incidence of TEAEs by 1-year time interval
- Incidence of TEAEs by total duration of exposure cohort (as per categories defined in Section 3.2.7)
- Incidence of TEAEs by study period (Up-Titration, Evaluation, Down-Titration, Safety)
- Incidence of TEAEs by maximum intensity
- Incidence of drug-related TEAEs
- Incidence of serious TEAEs
- Incidence of drug-related serious TEAEs
- Incidence of TEAEs for TEAEs occurring in at least 5% of subjects
- Incidence of TEAEs by 3-month time intervals for TEAEs occurring in at least 5% of subjects
- Incidence of TEAEs by 3-month time intervals for TEAEs occurring in at least 5% of subjects by geographical region
- Incidence of non-serious TEAEs occurring in at least 5% of subjects
- Incidence of non-serious TEAEs occurring in at least 5% of subjects by geographical region
- Incidence of drug-related TEAEs occurring in at least 5% of subjects
- Incidence of drug-related TEAEs occurring in at least 5% of subjects by geographical region
- Incidence of TEAEs leading to permanent discontinuation of BRV
- Incidence of drug-related TEAEs leading to permanent discontinuation of BRV

Tables presenting incidence of TEAEs occurring in at least 5% of subjects will include only TEAEs occurring on or above the reporting threshold of 5% in any age group or geographical region.

Additionally, following incidence tables will be presented by total duration of exposure categories:

- Incidence of serious TEAEs

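### An adverse event that began on BRV in the core study and then worsens, turns serious or ends BRV in N01266 can be left out of the primary TEAE tables, because SAP Section 3.10.1 classifies by onset date alone

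*SAP*

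**What the plan says.** Section 3.10.1 of the SAP allows two classes only: "AEs will be classified as either pre-treatment or treatment emergent". For this purpose, "first dose of BRV refers to the first dose in N01266", and the core-study dose is expressly excluded for LTFU subjects. The dividing rules are "Pre-treatment AEs are defined as AEs which had an onset date at least one day prior to the first dose of BRV" and "Treatment-emergent adverse events (TEAEs) are defined as AEs that had onset on or after the day of first BRV dose". There is one default for poor dates: "AEs with a missing onset date will also be classified as TEAEs provided the subject received at least one dose of BRV". Partial dates whose known part equals or follows the month or year of the first N01266 dose are treated the same way.

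The section has no clause for an event that is ongoing at that dose and later changes.

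The classification feeds the main safety output. Section 2.2.1 names treatment-emergent AEs and treatment-emergent SAEs as the primary variables. The overview in Section 8.2.1 has rows for serious, severe, drug-related and treatment-ending events, each limited to TEAEs. Section 8.2.2 does the same by system organ class and preferred term, for example "Incidence of TEAEs leading to permanent discontinuation of BRV".

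**The concern.** Under Section 2, LTFU subjects go straight into the Evaluation Period and stay on the dose they had at the end of the core study. Table 2-1 notes that their Entry Visit is the core study's final evaluation visit. For these children the first N01266 dose is an administrative point in continuing treatment. An event that started on BRV shortly before that point is not pre-treatment in any ordinary sense.

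What matters is how such an event is handled afterwards. The primary objective is long-term safety and tolerability. An event that persists from the core study and eventually becomes serious, or makes the child stop BRV, belongs in that picture. If the primary tables omit it, they can understate the result. The discontinuation table may also disagree with disposition (Section 5.1), which counts discontinuations by primary reason without a TEAE restriction. The SAP gives no explanation for such a difference.

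**Working it through.** The SAP is descriptive and states no event rate or formal sample size, so there is no figure to reproduce. The check applies the Section 3.10.1 rule to typical LTFU cases and follows each into the planned tables.

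**Inputs**
- Reference dose: first BRV dose in N01266 (Sections 3.2.1.1 and 3.10.1).
- Classes: two, by onset date only (Section 3.10.1).
- Treatment at entry: BRV continued from the core study (Section 2).
- Table scope: TEAEs only for the serious and discontinuation rows (Section 8.2.1) and for the incidence tables (Section 8.2.2).

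**Cases**
1. Full onset date in the core study, resolved before N01266: pre-treatment and not counted. This is reasonable, because the event belongs to the core study.
2. Full onset date in the core study, ongoing at entry, worsens or becomes serious in N01266 under the same record: pre-treatment. Absent from the TEAE and serious TEAE tables.
3. Full onset date in the core study, ongoing at entry, BRV permanently stopped for it in N01266: pre-treatment. Absent from the TEAE-discontinuation row and table.
4. Onset on or after the day of the first N01266 dose: TEAE, counted.
5. Onset date missing, or partial and matching the month or year of the first N01266 dose: TEAE, counted even if the event began in the core study.

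Cases 2 and 3 are the gap. Comparing case 5 with cases 2 and 3 shows that entry into the primary tables can depend on how completely the onset date was recorded: a vague date is counted and an exact one is not.

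**Could another table pick up cases 2 and 3?**
- Section 8.2.2 plans a 3-month table of events ongoing in each interval, but it covers TEAEs only.
- Section 8.2.2 also plans a subject-number table broken down by treatment-emergence, but that table is defined as identifying subjects with any TEAE.
- Section 8.2.3 (events of interest) is limited to TEAEs.
- The deaths row in Section 8.2.1 is not worded as limited to TEAEs, so deaths should be captured.
- Disposition in Section 5.1 can show case 3 under its primary reason.
- Section 3.1 promises listings of all documented data, so an event recorded in N01266 should be listed.

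Cases 2 and 3 can therefore be traced in the report but are not counted in the primary summaries.

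**Size of the group under the rule.** Section 2.4 plans about 600 subjects with at least 100 directly enrolled, so 600 − 100 gives up to about 500 LTFU subjects. The SAP does not say how many will have an ongoing event at entry, or how many of those events will worsen, become serious or end treatment.

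**The case against.** Four points deserve a fair hearing.

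**The reference dose is a deliberate choice.** Section 3.10.1 says plainly that it means the N01266 dose. This avoids counting core-study onsets a second time. That stands, and the fix leaves it alone. It does not supply a rule for ongoing events that change later.

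**The protocol may close part of the gap.** Whether worsening or new seriousness opens a new AE record with a new onset date is usually a protocol rule, and the protocol is not at hand. If it does, case 2 is captured. Case 3 is captured only if the event is also re-recorded when BRV is stopped without worsening. The concern about case 2 is therefore conditional.

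**The events are not lost from the report.** Listings, disposition and the deaths row remain, and missing or matching partial dates default to TEAE. This also stands. The omission concerns the primary summaries.

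**Some stronger inferences fail.** A reader might infer that the safety tables use two treatment starts, because LTFU Baseline for laboratory, vital-sign and ECG data is the "most recent measurement up to first BRV administration in core study, not in N01266 as in the general definition of Baseline values". That passage fixes a Baseline value. The counting of abnormal findings still runs in an N01266 window (Sections 3.2.1.1, 3.9, 8.3, 8.4.1 and 8.4.2), as it does for AEs. A reader might also infer that the rule biases LTFU rates against those of directly enrolled subjects. Section 3 plans no statistical comparison and analyses the cohorts separately as well as pooled. In addition, the early on-drug events of LTFU children fall in the core study under any N01266 definition, so changing this rule would not make the cohorts comparable.

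**Conclusion.** The point holds as a gap in the definition of the primary variable. A dated core-study event that is ongoing at entry and ends BRV in N01266 is left out of the discontinuation table unless it is re-recorded. One that worsens or becomes serious is left out if sites keep its existing record. The effect can only lower the reported counts, and it can leave the discontinuation table unreconciled with disposition.

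The size cannot be estimated from the document. A reader might want a percentage understatement, but every input would be invented. A subject who also has another qualifying TEAE would be counted in that row anyway.

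The conclusion rests on the SAP text alone and assumes no protocol rule that re-dates such events. It does not mean that slow intolerance goes unseen in general, since every event with onset in N01266 is counted. The gap should be closed in the SAP because the tables concerned serve the primary objective.

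**What to change.** Keep the first N01266 dose as the onset reference in Section 3.10.1 and make three changes.

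1. Add that an AE ongoing at the first N01266 dose counts as treatment-emergent if it increases in intensity or becomes serious on or after that dose.
2. In the overview, serious and discontinuation tables, include any AE that becomes serious or leads to permanent BRV discontinuation during N01266, whatever its onset date. Mark it with a core-study-onset flag where that applies, so that the tables reconcile with disposition in Section 5.1.
3. For LTFU subjects, relabel events with onset on BRV in the core study as core-study onset, and stop calling them pre-treatment.

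If the protocol already requires a new record on worsening or new seriousness, cite that rule; the first change then alters little.

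**Cost.** SAP wording, table programming and access to core-study AE records; Section 3.2.2 already refers to a Data Integration Plan for core-study data. The first change, and the seriousness part of the second, need the date on which intensity or seriousness changed. The SAP does not show that these dates are collected, so this should be checked. The discontinuation part needs no re-dating of onset. A few flagged events will also appear in the core study report, and the reported rates will be slightly less favourable.
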